Baseline autoimmune disease prevalence assessment. The enrollment questionnaire accompanied by a cover letter will be sent to all participants and will include a question regarding personal and family history of five specific autoimmune diseases (AITD, IBD, psoriasis, RA and PMR) as well as space to write in others. Individuals will also be asked about their family history of any autoimmune disease.

Screening for chronic daily knee pain during run-in. As VITAL participants will be involved in the parent trial of cancer and cardiovascular outcomes and potentially other ancillary studies, to limit participant burden we will screen the entire population and select 2000 participants with chronic daily and severe knee pain who are willing and eligible to be in this subtrial. This number will provide ample statistical power for chronic knee pain outcomes.

For our purposes, the outcomes of interest will be chronic frequent knee pain (not radiographic knee OA). We will thus screen our trial population and classify those with: knee pain with walking 2-3 blocks, a doctor's diagnosis of knee OA, pain > 5 days per week and for > one year and classify those with all four of these as having chronic frequent knee pain. (**Fig. 2**). Individuals with total knee replacements at baseline will be excluded. Our goal is to include only those with the most severe, chronic knee pain at baseline in this longitudinal RCT

[figure not shown]

Fig. 2. Screening for chronic severe knee pain during run-in

of the two investigational agents. Based on estimates of the prevalence of knee pain in a population of adults over age 60^{123, 404} and the added specificity of our screening questions, we anticipate that the prevalence of chronic severe knee pain by this method will be approximately 12.5%, or 5000 individuals of the 40,000 individuals in the run-in phase. Although the sensitivity and specificity of our screening questions for chronic frequent knee pain (highly likely to be OA) in this population is not known, it is likely higher than that of Lavalley and ultimately will ensure that we include individuals with chronic, frequent knee pain, regardless of diagnosis.

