Baseline knee pain severity assessment. We will include supplementary longitudinal knee pain assessment questions (**Appendix B**) and a cover letter with run-in questionnaire to 5000 individuals during the run-in phase. After the run-in phase, 50% of the individuals who were compliant with > 66% of study medications and supplementary requests, and continue to be willing and eligible, will be enrolled in VITAL. Thus, we anticipate that 2500 of the 5000 will be eligible for this sub-trial, and of these 2000 individuals with chronic, severe knee pain will complete the baseline assessment and will be followed annually. In a subset of 100 men and 100 women participants, we will request access to medical records and radiograph reports and have them forwarded to us for review to validate the sensitivity, specificity, positive and negative predictive value of our screening strategy for the diagnosis of knee OA. A standard definition of knee OA for epidemiologic studies will be employed: physician diagnosis of OA and the presence of one or more osteophytes on AP knee radiographs⁴⁰⁵.

Baseline Blood Collection and Randomization are those of the parent VITAL trial, described in Partners' IRB approved protocol 2009-P-00127; clinicaltrials.gov number 01169259.

Briefly describe study procedures. Include any local site restrictions, for example, "Subjects enrolled at Partners will not participate in the pharmacokinetic portion of the study." Describe study endpoints.

Trial Procedures and Data Collection

Treatment with active vitamin D3 and/or fish oil or placebo is described in Partners' IRB approved protocol 2009-P-00127; clinicaltrials.gov number 01169259.

Follow-up procedures, dietary and supplemental intake assessments, are those of the parent VITAL trial, described in Partners' IRB approved protocol 2009-P-00127; clinicaltrials.gov number 01169259.

Incident autoimmune disease ascertainment and validation. Incident autoimmune disease case identification during the trial will be a 2-stage procedure:

1. Questions inquiring about new onset autoimmune diseases will be sent with the annual

Table 3. Criteria for the Validation of Autoimmune diseases

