Autoimmune thyroid disease: Hashimoto's disease: 1) no prior thyroid surgery or I ¹³¹ therapy, TSH > 4.5 mu/L, and anti-TPO >20IU/mL; OR 2) no prior thyroid surgery or I ¹³¹ therapy, anti-TPO >20IU/mL and currently receiving levothyroxine therapy ⁴²⁸ . Graves' disease: NOT receiving levothyroxine and either: 1) TSH <0.5mU/L for ≥ 3 months, with diffuse goiter and anti-TPO; OR 2) TSH <0.5mU/L and diffuse uptake on radionuclide thyroid scan ⁴²⁷
Inflammatory bowel disease: Crohn's disease: ≥ 2 separated by ≥ 2 months: 1) abdominal pain, diarrhea, weight loss, malaise, and/or rectal bleeding; 2) endoscopic findings of linear ulceration, mucosal cobblestoning, skip areas, or perianal disease; 3) radiologic findings of fistula, stricture, mucosal cobblestoning, or ulceration; 4) laparotomy appearance of "creeping fat," bowel wall induration, mesenteric lymphadenopathy; 5) histologic transmural inflammation and/or epithelioid granulomas ⁴²⁸ . Ulcerative colitis: ≥ 2, separated by ≥ 6 months: 1) diffusely granular or friable colonic mucosa on endoscopy; AND 2) continuous mucosal involvement by endoscopy or barium studies ⁴²⁸ .
Polymyalgia rheumatica: 1) bilateral aching and morning stiffness (≥ 30 min) for ≥ 1 month involving: neck or torso, shoulders or proximal regions of the arms, and hips or proximal thighs; 2) ESR > 40 mm/hr (Westergren); AND 3) prompt response to corticosteroid therapy ¹¹⁹ ; AND/OR Giant cell arteritis: ≥ 3: 1) age > 50 years; 2) new headache; 3) temporal artery tenderness or decreased pulsation on exam; 4) elevated ESR; 5) temporal artery biopsy with vasculitis or granulomatous infiltration ¹⁴⁵ .
Psoriasis: Physician diagnosis of psoriasis in medical records ^{125, 429}
Rheumatoid Arthritis: ≥ 4 for ≥ 6 weeks: 1) morning stiffness > 60 minutes; 2) arthritis > 3 body areas; 3) hand arthritis; 4) symmetric arthritis; 5) rheumatoid nodules; 6) rheumatoid factor and/or anti-anti-cyclic citrullinated peptide antibodies; 7) radiographic changes ^{430, 431} .

questionnaires. Participants who self-report an incident autoimmune disease endpoints on any of these questionnaires.

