aires will be mailed a letter asking them to sign a medical release form authorizing VITAL staff to obtain hospital/physician records. The request will be accompanied by a cover letter expressing sympathy for the diagnosis and explaining guidelines and the scientific importance of record validation. Non-responders will be sent two additional requests for the medical release form. During the 10 year Women's Health Study trial, only 5% of cases refused to sign a medical release. After the release is obtained, a copy will be sent to the treating hospital or physician. If there is no response within 1 month, a second request will be mailed, followed by a phone call. In the Women's Health Study, the staff was able to obtain hospital/physician records 99% of the time.

2. Medical records will be reviewed independently by two trained physicians (including board certified rheumatologist, endocrinologist, and gastroenterologists) blinded to the randomized treatment assignment, will confirm or disconfirm the autoimmune disease according to classification criteria (**Table 3**). The specificity of autoimmune connective tissue disease detection using a staged series design is very high, reducing misclassification of healthy subjects⁴⁰⁶. Similar procedures have been used in the Nurses' Health Study for the validation of RA and SLE by self-report, with case confirmation rates of 69-70% of medical record reviewed^{386, 387}. All participants who report autoimmune diseases that cannot be validated will be censored from analyses at the time of the ambiguous self-report. The primary autoimmune disease endpoint of VITAL will be total autoimmune disease incidence. We estimate that 1000 or more new cases of autoimmune disease should occur during the five years of this trial in this elderly population, although we will not be able to capture them all. We anticipate some over-reporting of incident autoimmune diseases, and may need to mail up to three separate medical record requests in some cases. We estimate a final confirmation of 60% of the true incident cases, or 600 cases. Individuals who report an autoimmune disease at baseline or in follow-up will not be excluded from analyses of other incident autoimmune diseases (e.g., an individual who reported pre-existing AITD will not be excluded from analyses of new autoimmune diseases).

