When specimens or data collected by research collaborators outside Partners will be sent to Partners investigators, indicate from where the specimens/data will be obtained and whether the specimens/data will contain identifiers that could be used by Partners investigators to link the specimens/data to individual subjects. When appropriate, submit documentation of IRB approval and a copy of the IRB-approved consent form from the institution where the specimens/data were collected.

Not applicable.

Protocol Biostatistical Analyses

Separate analyses will be conducted for the 3 endpoints and for the 2 nutritional supplements, vitamin D and omega-3 fatty acids. Analyses of treatment effects will be based on the intent-to-treat principle. The first analysis will compare baseline characteristics by randomized treatment

assignment to ensure that balance was achieved by the randomization. Characteristics to be examined include known risk factors for autoimmune diseases, systemic inflammation, and chronic knee pain including: age; gender; race/ethnicity; family history of autoimmune disease; BMI; smoking; alcohol use; physical activity; co-morbid medical conditions such as hypertension, hyperlipidemia, diabetes, and cardiovascular disease; and baseline vitamin D and omega-3 fatty acid levels as assessed by dietary questionnaire in all participants and blood assays in the case-cohort subsample. The large sample size, as well as successful balance of known potential confounders, will provide assurance that unmeasured or unknown potential confounders will also be equally distributed across randomized treatment groups. For autoimmune disease, we will estimate the intervention effects on the primary endpoint of total incident autoimmune disease. For inflammatory biomarkers, we will assess changes in linear biomarkers (log transformed if necessary). For chronic knee pain, the primary endpoint will be assessed by the WOMAC pain scale; secondary analyses will test for decreases in WOMAC stiffness, function and global scales, as well as analgesic use separately. Data analyses will be performed using SAS 9.2 (SAS Institute Inc., Cary, North Carolina).

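### The primary endpoint is named total autoimmune disease, but Table 3 gives confirmation criteria for five disease groups only, so the endpoint analysed is a five-group composite

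*Combined protocol and SAP*

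**What the plan says.** All references are to the combined protocol and SAP.

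- **Endpoint.** The section on incident autoimmune disease ascertainment and validation says: "The primary autoimmune disease endpoint of VITAL will be total autoimmune disease incidence". Protocol Biostatistical Analyses repeats it: "we will estimate the intervention effects on the primary endpoint of total incident autoimmune disease". Neither place lists the diseases included.
- **Reporting.** The baseline prevalence assessment asks about "five specific autoimmune diseases (AITD, IBD, psoriasis, RA and PMR) as well as space to write in others". The annual follow-up question concerns new autoimmune disease in general. The background section introduces the same five diseases as examples, not as a complete list.
- **Confirmation.** Two physicians blinded to assignment "will confirm or disconfirm the autoimmune disease according to classification criteria", with a pointer to Table 3, "Criteria for the Validation of Autoimmune diseases". Its rows are autoimmune thyroid disease, inflammatory bowel disease, polymyalgia rheumatica with giant cell arteritis, psoriasis and rheumatoid arthritis. Most rows set detailed criteria; the psoriasis row asks only for "Physician diagnosis of psoriasis in medical records".
- **Unvalidated reports.** "All participants who report autoimmune diseases that cannot be validated will be censored from analyses at the time of the ambiguous self-report".
- **Later events.** The same section says that someone who reports one autoimmune disease, at baseline or in follow-up, stays in the analyses of other new autoimmune diseases. The power section adds that several diseases in one person are analysed as separate endpoints.

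**The concern.** The name of the endpoint and the intake of reports are open-ended, while the only criteria supplied are closed. A participant with a new, fully documented disease such as SLE has no Table 3 criterion to meet. The plan itself mentions SLE: it cites similar procedures used in another cohort "for the validation of RA and SLE by self-report". That is a precedent for the method and supplies no SLE criterion for this trial.

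Two things are at stake. The first is interpretation: a result on five disease groups would be reported as a result on total autoimmune disease. The second is conduct: without a rule, whether a written-in disease counts, is rejected or leads to censoring would have to be settled case by case during the trial. The question here is which diseases can count at all. It differs from how an unclear report of a listed disease should be handled.

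**Working it through.** **Step 1. Follow one case through the rules.** Take a participant who reports a new autoimmune disease outside Table 3 and whose records document it clearly.

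| Stage | Rule in the plan | Result for this case |
|---|---|---|
| Report | Annual question on new autoimmune disease | Can be reported |
| Review | Confirm or reject by Table 3 | No criterion exists, so it cannot be confirmed |
| Counting | Confirmed total autoimmune disease | Not a primary event |
| Time at risk, reading A | Any report that cannot be validated is censored | Censored at the report |
| Time at risk, reading B | Censoring covers only reports that records leave unclear | Rejected, stays at risk |
| Time at risk, later-events sentence | Reporting one disease does not exclude from analysis of others | Stays at risk for the five groups; conflicts with reading A |

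The counting row is the same under every reading. Only the handling of later time at risk is unsettled.

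**Step 2. Look for text that would let the case count.** The paragraph on consent and record review for this ancillary study speaks of published criteria without naming Table 3. It names no further disease and no further criteria, so it leaves the gap open.

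**Step 3. Reproduce the plan's power figure.** Inputs from Power calculations, part a: 20,000 participants, 5 years, 1000 cases per 100,000 per year, 60% confirmed, observed RR 0.70, stated power 0.81. The significance level is 0.05; its sidedness is not stated there, and two-sided is used here.

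- Expected cases: 20,000 × 5 × 1000/100,000 = 1000.
- Confirmed: 0.60 × 1000 = 600; per cell 600/4 = 150.
- Events, one active cell against double placebo: 150 × (1 + 0.70) = 255.
- Schoenfeld power: Φ(√255/2 × |ln 0.70| − 1.96) = Φ(2.848 − 1.96) = Φ(0.888) = 0.813.

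This agrees with the stated 0.81.

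**Step 4. Ask whether events are lost from that calculation.** The documents give no share for diseases outside the five groups. Assume 5% to 20%, for illustration only.

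*If the 600 included them* and they could not be confirmed, 30 to 120 cases would go (0.05 × 600 to 0.20 × 600), with these results:

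| Comparison | Control cases | Events | Power at RR 0.70 |
|---|---|---|---|
| Single cell, as planned | 150 | 255 | 0.813 |
| Single cell, 5% lost | 142.5 | 242.25 | 0.793 |
| Single cell, 20% lost | 120 | 204 | 0.721 |
| Main effect, as planned | 300 | 510 | 0.981 |
| Main effect, 5% lost | 285 | 484.5 | 0.975 |
| Main effect, 20% lost | 240 | 408 | 0.950 |

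The main-effect rows use two placebo-side cells, 2 × 150 = 300, with only one agent effective.

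*If the 600 excluded them*, nothing changes. The plan defines the 600 as cases remaining after confirmation, and a disease without a criterion cannot be among them. It would fall among the 1000 − 600 = 400 cases that the plan already expects not to confirm. If other diseases were 5% to 20% of the 1000, reaching 600 would need 600/950 = 63% to 600/800 = 75% of the listed cases to be confirmed, instead of 60% of all. Whether the incidence of 1000 covers more than the five groups cannot be checked, because Tables 1 and 2 are not in the text supplied.

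**The case against.** The strongest reply is that this is a loose label on a sound endpoint. A composite of five disease groups is valid, review is blinded and allocation is randomised, so the treatment comparison for that composite is not shown to be biased. That stands. It does not supply a sentence limiting the endpoint to five groups, and the wording elsewhere points the other way.

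A reader might go on to draw three stronger conclusions. The documents support none of them.

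- **Documented cases must be censored.** The censoring sentence is tied to an ambiguous self-report. A disease clearly documented in the records can be seen as rejected rather than ambiguous, with the person still at risk. Censoring is one reading only.
- **Later follow-up for the five groups is lost.** The later-events sentence and the separate-endpoints statement in the power section say otherwise. What is shown is a conflict with the censoring sentence.
- **The trial loses 30 to 120 events and some power.** Those cases would be taken from 600 that are already confirmed, using an assumed share. The arithmetic in step 4 is conditional on a premise that the plan's own definition of the 600 contradicts.

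It is also fair to say that Table 3 nowhere declares itself exclusive. The restriction is inferred from its being the only set of criteria given and the one to which reviewers are pointed.

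**Conclusion.** The point holds as a mismatch between the endpoint named and the endpoint that the rules produce. Under every reading of the censoring sentence, a documented incident autoimmune disease outside the five groups does not count, so the analysed endpoint is a five-group composite. The conclusion assumes that Table 3 is the complete set of criteria; nothing in the documents adds to it.

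Its size in events cannot be determined from the documents, and no loss of power or bias is established. The consequence is for what the trial may claim and for how reports of other diseases are handled. It is more than missing detail, because the stated confirmation rule changes the primary endpoint and the censoring sentence conflicts with the later-events sentence. It should be corrected.

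**What to change.** Choose one of two.

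**(a) Keep the total endpoint.** Add a Table 3 row for other autoimmune diseases, preferably a prespecified list so that it is clear which diseases qualify. Confirm them by physician diagnosis in the medical records, the standard that Table 3 already accepts for psoriasis, and count them in the total. State that records are requested for these diseases too, and check that the annual form, which is not in the text supplied, allows them to be reported. The small downside is a less strict criterion for a minority of cases.

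**(b) Restrict the endpoint.** Define it as incident autoimmune thyroid disease, inflammatory bowel disease, psoriasis, rheumatoid arthritis or polymyalgia rheumatica/giant cell arteritis, and limit conclusions to that composite. State that a report of any other disease neither counts as an event nor censors.

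Under either option, limit censoring to reports of endpoint diseases that the records cannot resolve, and reconcile that rule with the sentence keeping people who report one disease in the analyses of others. Also state whether the planning incidence and the 600 cases refer to the endpoint as then defined.

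The cost is one table row or one endpoint sentence, plus one sentence on censoring. Option (a) may add some record requests; option (b) adds none.

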Follow-up blood collection, biochemical assays for circulating 25(OH)D, EPA and DHA are those of the parent VITAL trial, described in Partners' IRB approved protocol 2009-P-00127; clinicaltrials.gov number 01169259.

Biochemical assays for Inflammatory biomarkers: IL-6, TNF receptor2 (TNFR2) and hsCRP assays. (Children's Hospital, Boston, MA, [name]) IL-6 will be measured by an ultra-sensitive quantitative sandwich enzyme immunoassay from R&D Systems. IL-6 is quantified in pg/ml and assay sensitivity is 0.94 pg/mL. IL-6 is a strong predictor of cardiovascular disease and type 2 diabetes^{23, 412, 413}, suggesting that a single sample represents long-term levels. $TNF\alpha$ cannot be reliably measured in stored plasma as it degrades rapidly. TNFR2 expression parallels $TNF\alpha$ levels and is a surrogate marker for inflammation^{414, 415}. TNFR2 will be measured by a quantitative sandwich ELISA assay from R & D Systems. Day-to-day assay variabilities at concentrations of 54.8, 252 and 356 pg/mL are 8.8, 3.7 and 5.8%, respectively. TNFR2 stability was assessed in 17 fresh blood samples, at baseline, and after a delay of 24 hours and 36 hours, and the CV was 0.8 for the comparison of 0 to 36 hours (personal communication, [name]). High sensitivity CRP will be measured by high sensitivity latex-enhanced immunonephelometric assay on a BNII analyzer (Dade Behring, Newark, Delaware), with a coefficient of variation of < 5%. CRP levels by this technique, in mg/L, are predictive of cardiovascular disease and type 2 diabetes in cohort studies^{23, 416}.

Knee Pain Assessments Among those who screen positive for chronic knee pain (knee pain with walking 2-3 blocks, pain > 5 days per week for > 1 year, and a doctor's diagnosis of knee OA and no history of total knee replacement) during the run-in phase, baseline knee pain symptoms will be assessed prior to randomization and receipt of any study medications. Thereafter, knee pain symptoms will be assessed annually during the same season (month) in this chronic knee pain subcohort of 2000 participants. We will use the following validated, short

instruments to assess knee pain, analgesic use and depression:

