a. Western Ontario McMaster Universities (WOMAC) Knee Osteoarthritis Index Developed in 1988, the WOMAC knee questionnaire is a multidimensional measure of pain, stiffness, and physical functional disability consisting of 24 items graded in a numerical rating scale ranging from 0 (“no symptoms”) to 10 (“extreme symptoms”)^{417, 418}. It is the most widely used and accepted measure for monitoring⁴¹⁹ the course of the disease or to determine the effectiveness of anti-rheumatic medications in many knee OA trials. As several studies pointed to redundancy in the WOMAC function scale^{68, 420}, Whitehouse and colleagues have developed and tested a reduced WOMAC function scale that contains seven functional items⁴²¹. This scale, when tested in 1578 total joint replacement patients, had a Cronbach’s alpha of 0.85 with the WOMAC, indicating reliability and responsiveness to change was even greater than that of the extended scale. We will utilize the reduced WOMAC function scale, along with the pain, stiffness, and overall WOMAC scales.

b. Analgesic medications Participants will be asked to report which medications they are taking from a short list of typical medications taken for knee pain, how frequently and for how long they have taken them. Medication use will be categorized as follows: (0) none, (1) acetaminophen/non-steroidal anti-inflammatory drugs (NSAIDs), (2) narcotics/adjunctive pain medications (such as anti-depressants and antiepileptics). A decrease in analgesic medication use (from higher to lower category) will be considered as a secondary outcome, and analgesic use will also be included as a covariate in other knee pain analyses.

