Inflammatory Biomarkers. In a randomly selected subcohort of 2000 participants, blood will be collected at both baseline and follow-up and changes in levels of plasma biomarkers of inflammation will be investigated. As inflammatory biomarkers are associated with age, BMI, medication use and cigarette smoking, we will again ensure that baseline characteristics are balanced in the four treatment groups in this subcohort and will additionally adjust for them in our analyses. Inflammatory Biomarkers (hsCRP, IL-6, TNFR2) will be analyzed as continuous outcomes. Descriptive statistics such as the minimum, maximum, range, median, and mean are used to summarize the variable as well as detect outliers and missing values. Exploratory graphical techniques such as Boxplots, Histograms, Quantile-Quantile plots, and Stem and Leaf plots will be used to further examine the distribution of each biomarker. Natural log transformation may be necessary based on our past analyses¹⁰⁵. Unadjusted treatment effects will be evaluated using two-way Analysis of Variance (ANOVA) or Kruskal–Wallis nonparametric test. Multiple linear regression will be used to test the association between the biomarkers (or transformed scale) and treatment groups, while adjusting for age and gender. Model assumptions and goodness of fit will be evaluated using applicable techniques³⁸⁷. In a secondary analysis, additional adjustment for the other potential predictors including baseline biomarkers will be performed.

Chronic Knee Pain. In a separate subcohort of approximately 2000 individuals with baseline chronic daily knee pain and no history of total knee replacement surgery, we will evaluate changes in level of knee pain over the course of the RCT. The annual measure of WOMAC knee pain subscale will be the primary outcome. Angst and colleagues examined data from 122 prospectively-followed individuals with knee OA in a comprehensive rehabilitation program to define the minimally clinically important difference (MCID) in WOMAC scores (range 0-10), for

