pain, stiffness and function³⁸⁸. Analgesic use will be secondary outcome, defined on a scale of 0-2: 0 (none), 1 (NSAIDs or acetaminophen only) and 2 (narcotics). As chronic knee pain is associated with age, BMI, medication use, comorbidities and depression (MHI-5), we will again ensure that baseline characteristics are balanced in the four treatment groups in this knee pain subcohort and will additionally adjust for these potential confounders in our analyses. Similarly, we will analyze repeated measures of WOMAC knee pain score, stiffness score, function score and globe score as continuous outcomes. The descriptive statistics and the distribution of each outcome variable will firstly be examined. Transformation will be considered if applicable. We will use two-way analysis of variance (ANOVA) or Kruskal–Wallis test for bivariable analysis and general linear mixed model for multivariable repeated measure analysis. For another secondary outcome, we will assess the effects of the supplements upon analgesic use, classified as: no medications, acetaminophen or non-steroidal use; and narcotic medication). Generalized linear mixed models for repeated binary outcomes will be used to examine the adjusted associations.

Statistical issues in resampling from a RCT. Our investigations of the effects of these agents on biomarkers of systemic inflammation and knee pain will not utilize the entire 20,000 individuals enrolled in the funded VITAL trial. Rather, each will follow a selected subcohort of approximately 2000 individuals. It is possible that these individuals will not be drawn completely equally or randomly from the 4 treatment groups. Possible unbalance of sample characteristics will be evaluated and be controlled for in multivariable analyses.

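### The plan does not say how baseline WOMAC pain enters the primary knee analysis and omits it from the named covariates, which may leave the Aim 3 estimate less precise than the data allow

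*Combined protocol and SAP*

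**What the plan says.** **Baseline is measured, and measured in time.** Under Knee Pain Assessments, for those who screen positive, "baseline knee pain symptoms will be assessed prior to randomization and receipt of any study medications". Under Baseline knee pain severity assessment, the subcohort is defined by completing it: "of these 2000 individuals with chronic, severe knee pain will complete the baseline assessment and will be followed annually". The score should therefore be available for nearly everyone analysed.

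**Outcome and model.** Under Protocol Biostatistical Analyses, Chronic Knee Pain, the aim is that "we will evaluate changes in level of knee pain over the course of the RCT". The outcome is defined as follows: "The annual measure of WOMAC knee pain subscale will be the primary outcome". The method is a "general linear mixed model for multivariable repeated measure analysis", preceded by a two-way ANOVA or Kruskal–Wallis test.

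**Covariates.** The same section gives the adjustment set: "As chronic knee pain is associated with age, BMI, medication use, comorbidities and depression (MHI-5"), and the plan "will additionally adjust for these potential confounders in our analyses". The item on analgesic medications adds that "analgesic use will also be included as a covariate in other knee pain analyses". No WOMAC score is named as a covariate in any knee analysis. None appears either in the opening list of characteristics to be compared between arms.

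**Related text.** Statistical issues in resampling from a RCT says that any imbalance found in the subcohorts will be examined and controlled for, without naming a variable. For Aim 2, by contrast, the baseline value of the outcome is named as an adjustment variable, though only in a secondary analysis.

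**The concern.** A participant's own earlier score on the same scale is usually among the strongest predictors of later scores. The protocol justifies collecting MHI-5 on the ground that mental health may account for part of the outcome variance, and that reasoning applies at least as well to baseline WOMAC pain.

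As written, an analyst could compare raw yearly scores, compare changes from baseline, put baseline into the response vector, or adjust for it, and claim to follow the plan each time. These choices give different estimates and different standard errors for both agents, and the choice could be made after the data are seen. At stake are the width of the Aim 3 interval, which matters most if the result is null, and the ability to detect effects below the MCID.

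**Working it through.** **Inputs from the documents.** WOMAC pain SD 2.25 and MCID 0.75 (Table 6); 2,000 participants followed for up to 5 years; 80% for loss to follow-up and compliance; type I error 0.05 and power 0.80 (Power calculations, Chronic knee pain).

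**Assumptions.** Two-sided testing (stated for Aim 2 only); four equal cells, so 2,000/4 × 0.8 = 400 per cell and 800 per arm for each agent's main effect; five yearly scores with the same SD as baseline; no other covariates. The correlation r is not in the documents.

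**1. The plan's own figures.** n per group = 2 × (1.96 + 0.84)² × (2.25/0.75)² = 142, as stated. With 400 per cell, SE = 2.25 × √(2/400) = 0.159 and 0.75/0.159 = 4.71, so power = Φ(4.71 − 1.96) = 0.997 (stated 0.99). The stated power therefore uses the full SD of a single score and takes no credit for baseline.

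**2. Equal correlation r between any two scores.** The effect is averaged over the five years. Per-person variance in units of SD²:

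- raw yearly scores: (1 + 4r)/5
- change from baseline: (1 + 4r)/5 + 1 − 2r
- baseline as covariate: (1 + 4r)/5 − r²

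SE = 2.25 × √(2v/800).

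| r | v: raw / change / adjusted | SE: raw / change / adjusted | cut v raw | cut v change |
|---|---|---|---|---|
| 0.3 | 0.44 / 0.84 / 0.35 | 0.0746 / 0.1031 / 0.0666 | 20% | 58% |
| 0.5 | 0.60 / 0.60 / 0.35 | 0.0871 / 0.0871 / 0.0666 | 42% | 42% |
| 0.7 | 0.76 / 0.36 / 0.27 | 0.0981 / 0.0675 / 0.0585 | 64% | 25% |

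At r = 0.5, the difference detectable with 80% power (2.80 × SE) falls from 0.24 to 0.19 points.

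**3. Baseline as a response.** Generalised least squares with the same inputs gives, at r = 0.3 / 0.5 / 0.7:

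- arm means free at baseline, with a change contrast: SE 0.1031 / 0.0871 / 0.0675, the same as for change scores
- arm means constrained equal at baseline: SE 0.0666 / 0.0666 / 0.0585, the same as for covariate adjustment

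**4. Correlation decaying yearly (AR(1), adjacent-year correlation r).** The raw variance is V = [5 + 2(4r + 3r² + 2r³ + r⁴)]/25, and the covariance of baseline with the five-year mean is c = (r + r² + r³ + r⁴ + r⁵)/5. Adjusted variance is V − c², so the cut against raw scores is c²/V.

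| r | V | c² | cut v raw |
|---|---|---|---|
| 0.4 | 0.379 | 0.017 | 5% |
| 0.5 | 0.445 | 0.038 | 8% |
| 0.6 | 0.523 | 0.077 | 15% |
| 0.7 | 0.616 | 0.151 | 24% |

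Change scores have variance V + 1 − 2c here. At r = 0.5 that is 0.445 + 1 − 0.3875 = 1.06, against 0.407 adjusted, so subtraction does worse still.

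**The case against.** A reader might infer that baseline WOMAC plays no part in the knee model. The documents do not support that. The section speaks of changes in knee pain, which requires a baseline as a subtracted value or as the first repeated measure, and the mixed model could hold it as a response. What can be shown is an unspecified role and an omission from the named covariates.

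Nor is every model with baseline as a response inefficient. Step 3 shows that the constrained version matches covariate adjustment. The plan does not say which version it intends.

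The larger variance cuts are also favourable cases. They compare with a model that has no covariates, whereas the plan adjusts for several. Analgesic use and MHI-5 plausibly share variance with baseline pain, so the added gain would be smaller. Equal correlation requires baseline to predict year 5 as well as year 1, and under AR(1) the gain over raw scores shrinks sharply. Selecting people with severe pain may also lower the correlation. All of this stands, and it is why a range is given.

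A chance baseline difference between arms (95% range ±1.96 × 2.25 × √(2/800) = ±0.22 points) should not be counted as a second harm. Under randomisation it is not bias, and the unadjusted standard error already includes it. The clause on imbalance could bring baseline WOMAC in, but it names no score, depends on the observed data, and gives no precision when the arms happen to be balanced.

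Finally, power at the MCID is hardly touched. That is correct, and no planned conclusion is shown to be invalid.

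**Conclusion.** The point holds as a gap in specification with a cost in precision. Baseline WOMAC pain is collected before randomisation in the people followed, is missing from the named covariates, and has no stated role. Precision is lost if it is left out, merely subtracted, or entered as an unconstrained response with a change contrast. If the analysts already intend a constrained-baseline model, nothing is lost except clarity.

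Under the assumptions listed, the variance cut against raw yearly scores runs from about 5% (AR(1), adjacent correlation 0.4) to about 64% (equal correlation 0.7), and is less to the extent that the planned covariates overlap with baseline pain. The correlation structure is an assumption throughout.

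It would be wrong to conclude that Aim 3 is underpowered for its stated target or that its estimate is biased. The benefit is a narrower interval, better sensitivity below 0.75 points, and one less choice left open until the data are in.

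**What to change.** In the Chronic Knee Pain part of Protocol Biostatistical Analyses, define the primary knee analysis as a mixed model of the yearly WOMAC pain scores after randomisation, with baseline WOMAC pain as a covariate whatever the observed balance. An equivalent choice is baseline as a response with arm means constrained equal at baseline. State one of the two. Specify the stiffness, function and global scores in the same way, each with its own baseline.

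The cost is a sentence or two in the analysis section. The scores are already being collected, so no further data or participants are required.
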